10.1 Primary Safety Endpoint

The primary safety endpoint of the study is defined as the Type I Complication Free Rate at 60 months (1800 days). Type I complications are adverse events caused by a component (i.e. pulse generator, electrode, EIT or programmer) of the S-ICD System that results in permanent loss of device function,²⁷ invasive intervention or death.

10.1.1 Primary Safety Endpoint Performance Goal

, the primary safety endpoint performance goal is 85.0%.

10.1.2 Primary Safety Endpoint Hypothesis

The primary safety endpoint null and alternative hypotheses are as follows:

Ho: The Type I Complication Free Rate at 60 months (p1) does not exceed the performance goal of 85.0%.

$$Ho: p1 \leq 85.0\%$$

Ha: The Type I Complication Free Rate at 60 months (p1) does exceed the performance goal of 85.0%.

$$Ha: p1 > 85.0\%$$

²⁷ *Permanent loss of device function* refers to: 1) the permanent loss of shock therapy and/or post shock pacing; 2) permanent loss of appropriate sensing in all available sensing configurations (oversensing that results in persistent inappropriate shocks or undersensing that could lead to undetected arrhythmias). Loss of device function includes programming the PG permanently off or temporarily off in advance of an explant/revision.

The null hypothesis will be rejected if the lower one-sided 95% confidence bound²⁸ of the Kaplan-Meier estimate, using the Peto method for standard error, exceeds the performance goal of 85.0%.

10.2 Secondary Safety Endpoint

The secondary safety endpoint of the study is defined as the Electrode-Related Complication Free Rate at 60 months. A complication is an adverse event that results in permanent loss of device function, invasive intervention or death. Electrode relatedness is defined in section 10.2.1.

10.2.1 Secondary Safety Endpoint Related Adverse events

The following complications occurring \leq 30 days after initial implant will be included in the secondary safety endpoint analysis if determined to be attributable to structural electrode failure OR occurring $>$ 30 days after implant regardless of cause:

- Electrode movement (>5 cm)
- Electrode impedance out of range
- Electrode conductor fracture
- Electrode deformation and/or breakage
- Electrode insulation failure

The following complications occurring $>$ 30 days after initial implant will be included in the secondary safety endpoint analysis if determined to be attributable to a structural electrode failure:

- Incomplete/improper electrode-header connection
- In-subject damage to electrode (e.g., accidental cut to electrode body during pocket revision, PG replacement, etc.)
- Electrode revisions to optimize therapy
- Electrode movement
- Infection
- Oversensing
- Undersensing

²⁸ Using the Peto estimate for the standard error.

10.2.2 Secondary Safety Endpoint Performance Goal

[REDACTED]
[REDACTED]
[REDACTED]
[REDACTED]
[REDACTED]
[REDACTED]
[REDACTED], the

primary safety endpoint performance goal is 92.5%.

10.2.3 Secondary Safety Endpoint Hypothesis

The primary safety endpoint null and alternative hypotheses are as follows:

Ho: The Electrode-Related Complication Free Rate at 60 months (p_1) does not exceed the performance goal of 92.5%.

$$Ho: p_1 \leq 92.5\%$$

Ha: The Electrode-Related Complication Free Rate at 60 months (p_1) does exceed the performance goal of 92.5%.

$$Ha: p_1 > 92.5\%$$

The null hypothesis will be rejected if the lower one-sided 95% confidence bound²⁹ of the Kaplan-Meier estimate using the Peto method for standard error exceeds the performance goal of 92.5%.

10.2.4 Individual Estimates for Secondary Safety Endpoint Related Events

[figure not shown]
In addition to the composite estimate of electrode related complications, individual rates of each adverse event category contributing to the primary safety endpoint will be examined including two-sided 95% exact confidence intervals.

²⁹ Using the Peto estimate for the standard error.

10.3 Primary Effectiveness Endpoint

The primary effectiveness endpoint of the study is defined as the Overall Shock Effectiveness in Converting Spontaneous Discrete Episodes of VT/VF through 60 months. Overall shock effectiveness refers to conversion of an episode following on any of the 5 shocks (maximum) that may be delivered during a single episode. Discrete episodes of VT/VF are those that are temporally independent (<3 within a 24 hour period), unlike storm episodes, which occur in clusters (≥ 3 episodes within a 24 hour period). Episodes that spontaneously terminate will be excluded from this endpoint since the effectiveness of the shock cannot be evaluated in such circumstances.

10.3.1 Primary Effectiveness Endpoint Performance Goal

10.3.2 Primary Effectiveness Endpoint Hypothesis

The primary effectiveness endpoint null and alternative hypotheses are as follows:

Ho: Overall Shock Effectiveness in Converting Spontaneous Discrete Episodes of VT/VF through 60 months (p_1) does not exceed the performance goal of 94.0%.

$$Ho: p_1 \leq 94.0\%$$

Ha: Overall Shock Effectiveness in Converting Spontaneous Discrete Episodes of VT/VF through 60 months (p_1) does exceed the performance goal of 94.0%.

[figure not shown]
$$Ha: p_1 > 94.0\%$$

The null hypothesis will be rejected if the lower one-sided 95% exact confidence bound of the estimate exceeds the performance goal of 94.0%.

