7.3 Revisions, Replacements and Explants

In the event that the electrode or PG is surgically revised after the initial implant procedure, the system revision form is used to record changes to the system. If either the PG or electrode is removed from service, a device status form must be completed for the out-of-service device(s). If the system is revised without replacing any system components, a system revision form is completed. If the PG or electrode is replaced, the new device(s) will be recorded on an additional implant form. **Table 9** lists all the data required for system revisions.

Table 9. System Revision Data Collection

Data Collection	Retention of Original Source Documentation
Adverse events, if applicable Newly implanted product and accessories utilized for S-ICD System (model/serial/lot/batch/etc.), if applicable	Investigational Center
Q-TECH Programmer Printouts: - Initial and Final Summary Reports - Captured S-ECG in each sensing vector, if sensing vector changed - Device episodes, if applicable Shocked induced VT/VF episodes (external ECG strips), ²³ if performed Chest x-ray(s) if applicable ²⁴	Investigational Center; upload copy to Cameron Health/BSC
SD Card Data (if new spontaneous episodes were recorded)	Cameron Health/BSC (e.g. via CAMELION)

²³ Induction testing is not required per protocol; upload only if performed. Any time induction testing is performed in the study, external ECG strips are only required for sustained ventricular arrhythmias that result in a shock, either from the S-ICD System or from an external defibrillator.

²⁴ An X-ray is not required per protocol; upload only if a chest x-ray of the S-ICD System was taken to assess the position of the S-ICD System, an S-ICD System-related adverse event, or suspected product issue.

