7.4 Study Completion

Subjects may be withdrawn from the study for a variety of reasons including:

- Subject withdraws consent for any reason;
- Subject is lost to follow-up despite best efforts to locate the subject;
- The S-ICD System is permanently explanted;
- The subject has been followed >60 months from the original implant date.

Subjects who undergo a permanent explant or who commence, but do not complete, an implant procedure should be contacted, either in person or by telephone, at least 30 days after the permanent explant or implant attempt in order to record any adverse events before being withdrawn from the study. The study completion form documents withdrawal of any subject from the study.

There are no additional follow-up requirements once a subject has been withdrawn from the study. **Table 10** lists all the data that are required for study completion.

Table 10. Study Completion Data Collection

Data Collection	Retention of Original Source Documentation
Adverse events, if applicable	Investigational Center
Q-TECH Programmer Printouts: - Initial and Final Summary Reports - Captured S-ECG in each sensing vector, if sensing vector changed - Device episodes, if applicable Shocked induced VT/VF episodes (external ECG strips), ²⁵ if performed Death letter, if applicable Chest x-ray(s) if applicable ²⁶	Investigational Center; upload copy to Cameron Health/BSC
SD Card Data (if new spontaneous episodes were recorded)	Cameron Health/BSC (e.g. via CAMELION)

²⁵ Induction testing is not required per protocol; upload only if performed. Any time induction testing is performed in the study, external ECG strips are only required for sustained ventricular arrhythmias that result in a shock, either from the S-ICD System or from an external defibrillator.

²⁶ An X-ray is not required per protocol; upload only if a chest x-ray of the S-ICD System was taken to assess the position of the S-ICD System, an S-ICD System-related adverse event, or suspected product issue.

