10. STATISTICAL CONSIDERATIONS

[figure not shown]
The S-ICD Post Approval Study is designed to examine the long-term safety and effectiveness of the S-ICD System. The study design includes two co-primary endpoints maintaining a family-wise significance level of 0.05 by defining a hierarchical testing procedure. The safety endpoint will be tested first. If the test is successful then the effectiveness endpoint will be tested at the same significance level. Primary endpoints will be tested prior to testing the secondary endpoints. Individual rates of each adverse event contributing to the primary safety endpoint will be examined including two-sided 95% exact confidence intervals. Other pre-specified observational analyses are defined to further investigate the long-term safety and effectiveness of the S-ICD System.

Subjects from the IDE study who provide informed consent for this study will be followed through 60 months post implant. All subjects enrolled in the S-ICD System Clinical Investigation (IDE G090013) who underwent an implant attempt will contribute to the analyses of the safety and effectiveness endpoints and additional analyses. Data from IDE subjects who do not provide consent for the study or subjects who previously exited the IDE will be censored at the time of IDE study exit in the endpoint analyses, but will not count toward the target enrollment sample size. All non-IDE subjects who undergo an implant procedure for the S-ICD System will be included in the endpoint analyses and will count toward the enrollment ceiling. All analyses may be done separately on IDE study subjects vs de novo implants. The statistical analyses related to this study will be executed by the sponsor and/or business partners working on behalf of the sponsor.

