10.4.1 Secondary Effectiveness Endpoint Performance Goal

10.4.2 Secondary Effectiveness Endpoint Hypothesis

The secondary effectiveness endpoint null and alternative hypotheses are as follows:

Ho: The First Shock Effectiveness in Converting Induced (Acute) and Spontaneous Discrete Episodes of VT/VF through 60 months (p_1) does not exceed the performance goal of 84.0%.

$$Ho: p_1 \leq 84.0\%$$

Ha: The First Shock Effectiveness in Converting Induced (Acute) and Spontaneous Discrete Episodes of VT/VF through 60 months (p_1) does exceed the performance goal of 84.0%.

$$Ha: p_1 > 84.0\%$$

The null hypothesis will be rejected if lower one-sided 95% exact confidence bound of the estimate exceeds the performance goal of 84.0%.

[figure not shown]

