10.7.4 Effectiveness Endpoint Analyses

The primary effectiveness endpoint of overall shock effectiveness for spontaneous discrete episodes of VT/VF will be examined using the binomial estimate including the one-sided 95% lower exact confidence bound.

³⁰ Peto method for standard error estimate

The secondary endpoint of first shock effectiveness for acute and spontaneous discrete episodes of VT/VF will be examined using the binomial estimate including the one-sided 95% lower exact confidence bound. If the difference in first shock effectiveness rate for the acute and spontaneous episodes is statistically significant at a 0.05 significant level using a chi-square test then separate analyses will be presented for first shock efficacy of induced and spontaneous episodes.

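### The primary effectiveness rule applies an exact binomial bound to pooled episodes as if they were independent, so its one-sided 5% level is not assured when subjects contribute repeated, correlated episodes

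*Combined protocol and SAP*

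**What the plan says.** Section 10.3 counts an episode as a success if any of up to five shocks converts it. Spontaneous discrete episodes through 60 months are counted, and self-terminating ones are left out. On what is discrete, it says: "Discrete episodes of VT/VF are those that are temporally independent (<3 within a 24 hour period"; three or more in 24 hours is a storm.

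Section 10.7.4 says that this endpoint "will be examined using the binomial estimate including the one-sided 95% lower exact confidence bound". Section 10.3.2 turns that into the decision: "The null hypothesis will be rejected if the lower one-sided 95% exact confidence bound of the estimate exceeds the performance goal of 94.0"%. Section 10 states the error rate that the design claims: "The study design includes two co-primary endpoints maintaining a family-wise significance level of 0.05 by defining a hierarchical testing procedure".

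Two operational sections bear on repeat episodes. The withdrawal reasons in 7.4 include consent withdrawal, loss to follow-up and "The S-ICD System is permanently explanted"; a failed conversion is not among them. Under 7.3, "If the PG or electrode is replaced, the new device(s) will be recorded on an additional implant form", so a subject can continue on a replacement device.

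Sections 10.3.1, 10.6.1 and 10.10 and Appendix D (Study Cohort Definitions) show no text. Section 10.7.8 is largely redacted and 10.7.9 is redacted.

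**The concern.** The exact bound is valid for independent trials with a common success probability. Here the trial is an episode, and several episodes can come from one subject. Anatomy, device position and disease are shared within a subject, so conversion may be correlated. Fewer than three episodes in 24 hours is a statement about timing. It removes storms, but it says nothing about a shared conversion probability, and two episodes on one day still both count.

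Positive correlation leaves the pooled estimate's variance larger than the binomial formula assumes, and the lower bound then sits too high. This is the pass/fail rule for a primary endpoint in a design that claims a 0.05 family-wise level. The risk is a declaration of more than 94% effectiveness, more often than 5% of the time, when the true rate is 94%.

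**Working it through.** **1. Inputs.** From the plan: goal 94.0%, one-sided 95% exact bound, episode as unit, follow-up to 60 months. Not visible, so assumed: 60, 100 or 200 contributing subjects; mean 1.3 to 3 episodes each; ICC 0 to 0.3; share of subjects who stop contributing after a failed episode.

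**2. The plan's own level under independence.** With x conversions in n episodes, the bound is the 5th percentile of Beta(x, n − x + 1). The largest failure counts that pass are 1/100, 4/150, 6/200, 8/250, 11/300 and 15/400. At a true 94%, the chance of passing is 0.0499 for n = 150, 0.0413 for n = 200 and 0.0305 for n = 400. The maximum over n = 49 to 1000 is 0.04995. So the rule holds 5% if episodes are independent.

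**3. What correlation does to one result.** With m episodes in every subject, the design effect is 1 + (m − 1) × ICC. For m = 2 and ICC 0.2 it is 1 + 1 × 0.2 = 1.2. At 194/200 the bound as planned is 94.2%, a pass. At an effective size of 200/1.2 = 166.7 it is 93.8%, a fail. The design effect that turns a pass into a fail is 1.09 for 6/200 failures, 1.47 for 5/200, 1.90 for 4/200, 2.38 for 3/200 and 2.85 for 6/300. Only results near the cut-off change.

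**4. Error of the planned rule, with 94% as the pooled episode rate.** Beta-binomial subjects, geometric episode counts, nobody stopping after a failure, ICC 0.1–0.3:

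| Mean episodes per subject | 100 subjects | 200 subjects |
|---|---|---|
| 1.5 | 4.1–5.0% | 4.5–5.8% |
| 2 | 4.8–7.0% | 5.5–8.3% |
| 3 | 6.8–11.6% | 7.0–12.6% |

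Repeat runs differ by up to about 0.7 points (100 subjects at mean 3 also gave 6.1–11.2%). At mean 1.3 with 100 subjects, error is 3.6–4.4%. At ICC 0.05 it is about 4–5% for means up to 2, and up to about 6% at mean 3. With no correlation it is 2.6–4.1%.

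**5. Effect of stopping after a failure, pooled rate held at 94%.** If half stop, error at means 1.5, 2 and 3 is 3.5–4.1%, 4.1–5.1% and 5.0–6.5% with 100 subjects, and 4.3–4.8%, 4.9–5.9% and 5.5–7.3% with 200. If all stop, it is 2.4–4.9% in every case run.

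**6. The other reading of 94%.** Suppose 94% is the average subject's conversion probability. Subjects who convert well then supply more episodes than those who stop at a failure, and the pooled estimate is biased upward. With 100 subjects, ICC 0.2 and all stopping, error is 9.5% at mean 2 and 21.7% at mean 3. A clustered bound gives 9.1% and 20.1%, so it does not cure this bias.

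**7. The clustered bound under the pooled-rate reading.** For the 100-subject column above, error falls to 3.8–4.2%, 4.3–5.0% and 5.0–7.0%. With 60 subjects at mean 3 it is 4.4–7.2%.

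**The case against.** The strongest reply is that every deciding input is unseen. ICC, episodes per subject and the number of contributing subjects are assumptions. The text not shown could contain a counting or cohort rule that limits episodes per subject. Exact bounds are also conservative, which absorbs mild correlation. All of this stands, and it limits the point to the visible rule. A hidden sensitivity analysis, by contrast, would leave that rule unchanged.

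A second reply is that the clustered bound is approximate and costs power, so it belongs in a sensitivity analysis. That is a defensible preference. But a sensitivity analysis does not support the 0.05 level claimed for the deciding test.

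A reader might infer that the plan's error rate does exceed 5%. The documents do not support that: with few repeats or low correlation the planned rule stays at or below about 5%. A reader might equally infer that the rule is safe whenever subjects stop at a failed episode. That holds only if 94% means the pooled episode rate (step 6).

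A reader might also extend the point to the chi-square comparison in 10.7.4. That test decides only whether induced and spontaneous results are shown separately and makes no success claim, so no change is asked for.

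**Conclusion.** The point holds as a conditional one: under the visible rule the one-sided 5% level is not assured. Error above 5% needs positive within-subject correlation together with frequent repeat episodes and, under the pooled-rate reading, enough subjects who continue after a failure. When these hold, error with 100–200 subjects is about 5–8% at a mean of 2 episodes and 7–13% at a mean of 3, for an assumed ICC of 0.1–0.3. At a mean of 1.5 it is about 4–6%, hardly a departure. The pooled rate is the natural reading of 10.3.2, but the plan should say so, because the role of stopping depends on it. Confidence is medium, since the inputs that fix the size are not public.

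**What to change.** In 10.3.2 and 10.7.4:

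- State that the estimand is the pooled episode conversion rate.
- Base the decision on a subject-clustered one-sided 95% lower bound, for example the exact bound at n/design effect. Take the design effect from the subject-level ratio estimator, floor it at 1, and set it to 1 if there are no failures.
- State that this reduces excess error but does not guarantee 5% (up to about 7% in the cases run).
- Pre-specify the exact bound on the first eligible episode per subject as a sensitivity check. Its error was at most 4.4%, but at a true 98% its power is only about 40–41% with 100 subjects (89–90% with 200), so it should not be the rule.
- Report the number of contributing subjects, the distribution of episodes per subject, and how many subjects contributed after a failed episode.

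Using the same bound for the secondary endpoint in 10.4.2 is optional. With an assumed 1,000–1,500 induced episodes, one per subject, the effect there is smaller (5.6–7.8% at mean 3).

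The cost is wording, a little code and some power; no new data or patients are needed. At an assumed true 98%, 100 subjects, mean 2 and none stopping, power goes from 86.5% to 85.2% with no correlation, 84.8% to 78.2% at ICC 0.1, and 82.3% to 69.0% at ICC 0.3. With 200 subjects at ICC 0.3 it goes from 98.0% to 90.7%. The sponsor should check these figures against its own sample-size assumptions.

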10.4 Secondary Effectiveness Endpoint

The secondary effectiveness endpoint of the study is defined as First Shock Effectiveness in Converting Induced (Acute) and Spontaneous Discrete Episodes of VT/VF through 60 months. Induced episodes following the initial implant procedure after enrollment (i.e., acute) will be counted towards the endpoint using the first shock delivered in the final position and final polarity. Because VT/VF induction test shocks are expected to be delivered at an energy below 80 J (e.g., 65 J), poolability with spontaneous episode shocks (all delivered at 80 J, non-programmable) will be assessed for the primary analysis. If the two data sets differ, separate analyses will be presented for first shock efficacy of induced episodes and first shock efficacy of spontaneous episodes.

10.4.1 Secondary Effectiveness Endpoint Performance Goal

10.4.2 Secondary Effectiveness Endpoint Hypothesis

The secondary effectiveness endpoint null and alternative hypotheses are as follows:

Ho: The First Shock Effectiveness in Converting Induced (Acute) and Spontaneous Discrete Episodes of VT/VF through 60 months (p_1) does not exceed the performance goal of 84.0%.

$$Ho: p_1 \leq 84.0\%$$

Ha: The First Shock Effectiveness in Converting Induced (Acute) and Spontaneous Discrete Episodes of VT/VF through 60 months (p_1) does exceed the performance goal of 84.0%.

$$Ha: p_1 > 84.0\%$$

The null hypothesis will be rejected if lower one-sided 95% exact confidence bound of the estimate exceeds the performance goal of 84.0%.

[figure not shown]
10.5 Additional Pre-Specified Effectiveness Analyses

Other effectiveness objectives that will be collected and analyzed are as follows:

- Implant test analysis (induced episode VT/VF conversion, VT/VF detection sensitivity and time to therapy)
- Spontaneous episodes of VT/VF
 - Incidence
 - Rhythm and rate
 - Time to therapy (treated episodes only)
 - Conversion rate for spontaneous VT/VF storms

10.6 Sample Size Determination

The MINITAB software, version 14.0 was used to calculate the sample size in this study.

10.6.1 Target Sample Size

10.7 Data Analysis

10.7.1 Safety Endpoint Analyses

The primary safety endpoint will be evaluated as the proportion of subjects free from Type I Complication at 60 months based on the Kaplan-Meier method including the one-sided lower 95% confidence interval.³⁰

The secondary safety endpoint will be evaluated as the proportion of subjects free from Electrode Related Complication at 60 months based on the Kaplan-Meier method including the one-sided lower 95% confidence interval.³⁰

The Kaplan-Meier analysis will take into account the time from implant until the occurrence of the complication and data from any subjects who are complication-free will be right censored at the last known follow-up including subjects who exited the study.

